6. STUDY SUBJECTS

Subject Profiles will be created for a subset of the data collected. Profiles are similar to data listings however instead of listing clinical data by the type of data, profiles will list the data by subject in order to provide a comprehensive overview of the clinical status of each subject.

6.1 Disposition of Subjects

The disposition of enrolled subjects throughout the study will be listed and summarized in tables.

The numbers and percentages of subjects enrolled, completed, discontinued from immunosuppression withdrawal, terminated from protocol, in each analysis population, as well as reasons for terminating the protocol early will be presented. For subjects discontinuing immunosuppression withdrawal early, the reasons for discontinuing withdrawal early will also be presented. Analysis populations will be derived according to the definitions in Section 5.

Reasons for terminating the study early include:

- ‘Voluntary Withdrawal’
- ‘Death’
- ‘Lost to Follow Up’
- ‘Adverse Event’
- ‘Protocol Deviation’

- ‘Other’

Reasons for discontinuing study medication/treatment early include:

- ‘Protocol Deviation’
- ‘Voluntary Discontinuation from Weaning’
- ‘Terminated from Study’
- ‘Second episode of mild rejection not requiring treatment’
- ‘Any episode of Rejection (mild, moderate, or severe) requiring treatment’
- ‘Chronic rejection’
- ‘Requirement for use of corticosteroid bolus therapy’
- ‘Abnormal LFTs in the absence of biopsy-proven rejection that do not substantially improve within maximum interval’
- ‘Other’

6.2 Protocol Deviations

Protocol deviations will be listed by site and subject with information such as deviation date and who identified it, deviation type and details, steps taken to resolve the deviation, and an indicator for whether the subject will continue in the trial. Protocol deviations will also be summarized in tabular format. The summary will be reported by clinical phenotype and will include the total number of protocol deviations, the number of subjects with at least one deviation, and indicators for whether the deviation was an inclusion/exclusion criteria deviation and whether the subject will continue in the trial.

7. DEMOGRAPHIC AND OTHER BASELINE CHARACTERISTICS

7.1 Recipient and Donor Demographics

Summary descriptive statistics for demographic characteristics will be reported for the ITT sample, the PP1, and the PP2 sample by clinical phenotype.

Demographic data will include age at transplant, age at enrollment, sex, race (primary and secondary), ethnicity, weight at enrollment, and height; these data will be presented separately for recipients and donors in the following manner:

- Continuous data (e.g., age, body weight, and height) will be summarized descriptively by mean, standard deviation, median, and range as well as categorized into groups (e.g., Age of donors (years): 18-33, 34-49, 50-65)
- Categorical data (e.g., sex, race, and ethnicity) will be presented as frequencies and percentages.

Recipient demographic data will also be presented in a data listing by site and subject and will include birth date, age at enrollment, sex, primary and secondary race, ethnicity, height,

weight and BMI. Donor demographic data will be presented in a data listing by site and subject and will include birth date, age at enrollment, sex, primary and secondary race, and ethnicity.

8. MEASUREMENTS OF TREATMENT COMPLIANCE

Compliance to immunosuppression withdrawal schedules will be presented in a data listing by subject and dose interval and will include dose, frequency, start date, stop date, duration, expected duration per protocol, and tapering status for dose interval. Expected duration per protocol for each dose interval is described above in Figure 1 (Section 3.6).

9. EFFICACY EVALUATION

9.1 Overview of Efficacy Analysis Issues

9.1.1 Handling of Dropouts or Missing Data

All efforts will be made via the querying and monitoring phases to avoid missing data. In general, missing data will not be imputed.

Missing endpoint data for Kaplan-Meier analyses (time off immunosuppression) will be accounted for by censoring the data after the last time point where the subject's relevant endpoints are known. This approach allows all subjects to contribute data at all points where subject's treatment response are known, excluding them only when their data is unknown.

Endpoint data that is missing due to the subject being lost to follow-up will be imputed as failures in the primary endpoint analysis.

9.1.2 Multicenter Studies

Study subjects will be recruited from 3 study sites. Due to the small number of subjects in the study, study data will be analyzed as a whole and no formal accommodation for site-to-site variation will be made. If any one site is a large enroller, basic descriptive analyses of baseline demographics, physical examination findings, medical history, and key study endpoints will be repeated for each site individually in order to allow qualitative exploration of site-to-site variability.

9.1.3 Assessment Time Windows

All visits, except as noted below, should be completed within ± 2 weeks of the scheduled time points in the Schedule of Events.

-Screening

- Interval between visits -2 and -1 will not exceed 9 weeks.
- Interval between visits -1 and 0 will not exceed 2 weeks.

-Initiation or interruption of gradual withdrawal of immunosuppression

- Immunosuppression withdrawal (visit 0) may begin on the same day as the liver biopsy

(visit -1) or up to 2 weeks afterwards.

- Additional monitoring at the current immunosuppression dose level may be indicated before continuing with the gradual withdrawal of immunosuppression. If so, the maximum interruption period may not exceed 4 weeks (see section 5.1).

- Liver biopsies

- A liver biopsy to determine eligibility at screening (visit -1) may be performed no later than 9 weeks after the initial screening visit (visit -2).
- If a for-cause biopsy is performed within 6 weeks of a scheduled study visit that includes a protocol biopsy, then all the tests (including ITN Core Laboratory blood draws, clinical assessments, etc.) for the scheduled visit can be conducted at the time as the for-cause biopsy.
- For subjects who have successfully withdrawn from immunosuppression, a biopsy will be performed within 4 to 8 weeks after the last dose of immunosuppressant was taken. In order for the biopsy to be performed within this time period, the window for the visit on which this biopsy occurs will be extended to ± 6 weeks.

Unscheduled visits may also occur throughout the study.

Measurements from unscheduled visits, scheduled visits obtained outside the scheduled assessment time windows, and windowed measurements not closest to the scheduled target day will be included in listings only and not in by-visit tabular displays.

9.2 Efficacy Variables

9.2.1 Primary Efficacy Variable

The proportion of subjects who are successfully withdrawn from immunosuppression, defined as those who remain off immunosuppression for at least 1 year. Subjects with acute rejection occurring after 1 year following complete immunosuppression withdrawal will be considered successfully withdrawn for the purpose of the primary endpoint.

9.2.2 Secondary Efficacy Variables

1) Immunosuppression-free duration: a continuous variable measured in days and is defined as: date of end of trial participation or date of restarting immunosuppression – date of completing withdrawal. All subjects completing withdrawal at any time will be included.

2) Time to Rejection: time from initiation of immunosuppression withdrawal to first episode of acute rejection or first diagnosis of chronic rejection measured in days and defined as date of first episode of acute rejection or date of first diagnosis of chronic rejection – date of

initiation of immunosuppression withdrawal. All subjects initiating withdrawal (PP1 sample) will be included.

3) Graft Loss or Death:

Proportion of subjects who have graft loss or who die after initiation of immunosuppression withdrawal: a continuous variable taking on values between 0 and 1, the numerator is the total number of subjects who experience either graft loss or death after initiation of immunosuppression withdrawal and the denominator is the total number of subjects initiating immunosuppression withdrawal (PP1 sample). This analysis will also be done on the PP2 sample.

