#### **1.3.2 Unique Immunobiology of the Liver**

Of all solid organs that are transplanted, the liver has been regarded historically and consistently as being immunologically privileged—the most resistant to immunologic attack and damage. Presentation of antigens via the portal venous system has long been recognized as more likely to result in a tolerizing response than presentation via the systemic venous system. In several allogeneic models ranging from rodent to canine to swine, minimal or even no exposure to immunosuppression has resulted in successful and durable graft function after transplantation.

In the human arena, the liver is unique among transplanted solid organs in several ways. First, while episodes of acute rejection commonly connote deleterious outcomes for nearly all other solid organs that we transplant, acute rejection after liver transplantation has had no such long-term connotations. Second, it is well known that some episodes of acute rejection may resolve spontaneously without treatment. Third, although chronic rejection in varied manifestations represents a major threat to the longevity of other transplanted solid organs, its incidence and therefore, its importance, is substantially less in the post-liver-transplant setting, particularly in the age of modern immunosuppression. Furthermore, it has been suggested that the advent of tacrolimus immunosuppression has nearly eliminated the threat of chronic rejection for pediatric liver transplant recipients, and that living-donor liver transplants may be particularly immune to chronic rejection. Finally, while the importance of humoral mechanisms of acute and chronic allograft has recently emerged for other solid organs, there is little literature to substantiate their relevance and importance in the setting of liver transplantation.

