#### **3.3.2 Secondary Endpoints**

##### **3.3.2.1 Safety of Immunosuppression Withdrawal**

1. The proportion of participants who have graft loss or who die after initiation of immunosuppression withdrawal.
2. The time from the start of immunosuppression withdrawal to
  - a. the first episode of acute rejection requiring treatment,
  - b. the second episode of acute rejection not requiring treatment, or
  - c. the diagnosis of chronic rejection.
3. The distribution of histologic severity among rejection episodes.
4. The incidence of adverse events.
5. Changes in renal function, blood pressure, cholesterol level, and glucose control.

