### 5.3.2 Discontinuation of Study Intervention

Immunosuppression withdrawal will be discontinued for a participant if he or she experiences any of the following:

- A second episode of mild rejection not requiring treatment.
- Any episode of rejection (mild, moderate, or severe) requiring treatment.
- Chronic rejection.
- Abnormal LFTs in the absence of biopsy-proven rejection that do not substantially improve (see section 5.5.2) within the maximum interval specified in section 5.3.1, Interruption of Study Intervention.

Such participants will be considered to have failed immunosuppression withdrawal.

Participants who fail immunosuppression withdrawal will move into the medium-intensity follow-up schedule (see Appendix 2) for 52 weeks after their LFTs have improved (see section 5.5.2) and then will be discharged from the study.

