#### **5.5.3.2 Mild Rejection Not Requiring Treatment**

Mild rejection will be treated as clinically indicated at the discretion of the investigator; management will depend on the results of additional follow-up as outlined in Figure 2.

If this is the first episode of mild rejection and it resolves without treatment, the participant may resume immunosuppression withdrawal at the same dose and level at which withdrawal was interrupted.

If this is the second episode of mild rejection not requiring treatment, the participant will not be permitted to resume tapering and will be considered to have failed immunosuppression withdrawal (see section 5.3).

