#### **9.2.2 Analysis of Secondary Endpoints**

##### **9.2.2.1 Safety of Immunosuppression Withdrawal**

The following endpoints will be analyzed using the PP and ITT samples:

- The proportion of participants who have graft loss or who die after initiation of immunosuppression withdrawal will be descriptively summarized with a two-sided, 95% CI.
- Median time from initiation of immunosuppression withdrawal to first episode of acute rejection or to first diagnosis of chronic rejection, with a corresponding two-sided 95% CI, will be estimated using the Kaplan-Meier method.
- Distribution of severity among rejection episodes and the incidence of adverse events will be descriptively summarized using frequency tables with enumerations and percentages.
- Descriptive statistics (mean, standard deviation, mean change from baseline) for renal function, blood pressure, cholesterol level, and glucose control over time will be presented.

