3.2.2 Secondary Endpoints

The following secondary endpoints are related to the safety of immunosuppression withdrawal.

- The proportion of subjects who have graft loss or who die after initiation of immunosuppression withdrawal.
- The time from the start of immunosuppression withdrawal to
 - the first episode of acute rejection requiring treatment,
 - the second episode of acute rejection not requiring treatment, or
 - the diagnosis of chronic rejection.
- The distribution of histologic severity among rejection episodes.
- The incidence of adverse events.
- Changes in renal function, blood pressure, cholesterol level, and glucose control.

Other secondary endpoints include

- Immunosuppression-free duration, defined as the time from discontinuation of immunosuppression to end of trial participation or to time of restarting immunosuppression;
- Results of mechanistic studies and clinical assessments at various time points that allow for the definition of profiles associated with tolerance;
- Results of mechanistic studies and clinical assessments that allow for definition of profiles associated with liver allograft rejection.

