9.3.2 Secondary Efficacy Analyses

- 1) Median immunosuppression-free duration will be estimated for all subjects completing withdrawal. Duration will be displayed graphically with a Kaplan-Meier curve and the corresponding median and two-sided 95% confidence interval.
- 2) Median time from initiation of immunosuppression withdrawal to first episode of acute rejection or to first diagnosis of chronic rejection will be estimated for the PP1 sample. Duration will be displayed graphically with a Kaplan-Meier curve and the corresponding median and two-sided 95% confidence interval.
- 3) The proportion of subjects experiencing graft loss or death after initiation of immunosuppression withdrawal will be descriptively summarized for the PP1 and PP2 samples as well as the ITT sample with 95% confidence intervals using an exact binomial method.

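### The time-to-rejection analysis counts any first acute rejection, so the three-part rejection endpoint that the plan defines is never estimated

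*SAP*

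**What the plan says.** Two descriptions of the same secondary endpoint stand side by side in each document.

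- **Endpoint sections.** Protocol 3.3.2.1 item 2 and SAP 3.2.2 give the same three parts, timed from the start of withdrawal: (a) "the first episode of acute rejection requiring treatment"; (b) "the second episode of acute rejection not requiring treatment, or" (c) chronic rejection.
- **Analysis sections.** Protocol 9.2.2.1 plans a Kaplan-Meier estimate of "Median time from initiation of immunosuppression withdrawal to first episode of acute rejection or to first diagnosis of chronic rejection". SAP 9.2.2 item 2 defines the variable as "time from initiation of immunosuppression withdrawal to first episode of acute rejection or first diagnosis of chronic rejection measured in days", and SAP 9.3.2 item 2 says that the median time "to first episode of acute rejection or to first diagnosis of chronic rejection will be estimated for the PP1 sample". SAP Table 9-1 has a single time-to-rejection row.

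The only general rule on rejection episodes, in SAP section 4, makes the central pathology read decisive. It adds no condition about treatment. SAP section 14, on changes from the protocol, does not mention the difference.

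**The concern.** Part (b) enters no time-to-event analysis, and part (a) loses its treatment condition. Only chronic rejection is the same in both descriptions.

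The case that separates them is one the trial expects. Protocol 5.5.3.2 states: "If this is the first episode of mild rejection and it resolves without treatment, the participant may resume immunosuppression withdrawal". Protocol 1.3.2 adds that "it is well known that some episodes of acute rejection may resolve spontaneously without treatment". A participant with one such episode has had an event in the planned analysis but not yet under the endpoint. If a treated rejection follows, its date enters no rejection time-to-event estimate.

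The defined event also has a clear purpose. Its parts follow the rejection-based reasons for stopping withdrawal in protocol 5.3.2, which include "A second episode of mild rejection not requiring treatment". The planned event counts some participants who, under the protocol, have not failed.

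At stake is a stated safety endpoint that would be reported under a different definition.

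**Working it through.** **1. Is the defined endpoint estimated elsewhere?**

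- Immunosuppression-free duration (SAP 9.2.2 item 1) starts at completion of withdrawal and leaves out everyone who never completes it.
- SAP 6.1 counts reasons for stopping withdrawal, without times.
- SAP 10.4.4 is a listing of allograft dysfunction episodes, with treatment status.

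None of these is a time-to-event estimate of the three-part event.

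**2. Direction.** Take the three parts as a composite and use the same centrally read episodes for both definitions. Any event under (a) or (b) implies a first acute episode on or before that date, and (c) is in both. So the planned analysis has an equal or larger number of events and, for each participant, an equal or earlier event time.

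The median need not follow that order, because censoring between the two dates changes the risk sets. Suppose A has an event at time 1 (planned) or 3 (defined), B is censored at 2, and C has an event at 5.

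- Planned: S(1) = 2/3 = 0.67, and the median is 5.
- Defined: S(3) = 1/2 = 0.50, and the median is 3 (or 4 if the flat stretch from 3 to 5 is split).

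**3. Size.** The plan gives no figure for this endpoint to reproduce. Its only precision figures, the exact intervals for 9/20 and 4/20, concern the primary endpoint; they reproduce (23.1% to 68.5% and 5.7% to 43.7%).

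Inputs:
- n = 20.
- p, the share of participants with acute rejection, from the protocol's paediatric series: 8/67 = 0.12 (elective) and 20/115 = 0.17 (all) in section 1.2.3.3; 7/50 = 0.14 in Table 2; 16/63 = 0.25 in Table 3. The 43% in section 1.2.3.4 is the adult figure from Table 2 and is not used.
- f, the share of those who reject whose only episode is untreated. The documents do not give it; I assume 0%, 25% and 50%.

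Formulas, with no earlier censoring and independent participants:
- expected rejecters = 20p
- expected gap in the event-free curve, in points = 100pf
- chance that at least one of 20 is counted differently = 1 − (1 − pf)^20

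| p | 20p | gap, f = 25% | chance, f = 25% | gap, f = 50% | chance, f = 50% |
|---|---|---|---|---|---|
| 0.12 | 2.4 | 3.0 | 0.456 | 6.0 | 0.710 |
| 0.14 | 2.8 | 3.5 | 0.510 | 7.0 | 0.766 |
| 0.17 | 3.4 | 4.25 | 0.580 | 8.5 | 0.831 |
| 0.25 | 5.0 | 6.25 | 0.725 | 12.5 | 0.931 |

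At f = 0 the gap and the chance are both 0. One participant is 1/20 = 5 points. For example, 5 planned events leave 1 − 5/20 = 0.75; if 2 of the 5 had only an untreated episode, the defined curve ends at 1 − 3/20 = 0.85.

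**4. Can it change whether a median is reported?** With 3 of 20 censored first (an assumption), 9 events leave 8/17 = 0.47, so the median is reached. Seven events leave 10/17 = 0.59, so it is not.

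**The case against.** The strongest reply is that the reported statistic may not change. The planned summary is a median. Five rejections without censoring leave the curve at 0.75, and with 3 censored first at 12/17 = 0.71. Five events reach the median only if at least 10 participants are censored before them. The 9-versus-7 example needs 45% with an event, above every paediatric rate used here. **This stands in part:** at those rates the median would usually be unreached under both definitions, and only the curve would differ. But the rates are not ceilings. In two of the series 37% and 46% were still weaning, and protocol 1.2.4.3 commits only to a success rate of at least 20%.

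The inputs are also weak. The 8/67 group is part of the 20/115, and the 16/63 series comes from the same centre. Table 3 reports that all episodes in the 16/63 series were treated, and the 7 of 50 are described as having failed weaning, so neither series supports a share above zero. Table 4 shows that neither paediatric programme took biopsies before or after withdrawal, as this trial does. **This stands:** the ranges are illustrations, and zero is possible.

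The analysis sections of the two documents agree with each other, so amending the endpoint definition would also remove the inconsistency. **True,** but the defined event appears in both endpoint sections and matches protocol 5.3.2. The match with 5.5.3.3 is looser, because that section stops withdrawal for moderate or severe rejection without naming treatment.

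Finally, the episode data are collected, so the defined time could be derived later. **That makes the fix cheap;** it does not put the analysis in the plan.

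**Conclusion.** The concern holds, and the plan should be corrected. Protocol 9.2.2.1 and SAP 9.2.2 and 9.3.2 analyse a broader event than the one defined in protocol 3.3.2.1 and SAP 3.2.2. Time to any first rejection is a legitimate measure, but it is not the stated endpoint.

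The numerical effect cannot be fixed from the documents. It is nil if no participant has an untreated first episode. If a quarter of those who reject have only an untreated episode, the expected gap is 3.0 to 6.25 points; at half, 6.0 to 12.5 points. This assumes the protocol's paediatric rates apply and no earlier censoring, and it is not a firm bound. I claim no direction for the median.

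The consequence is confined to one descriptive secondary safety endpoint. The primary result, the sample size and the stopping rules do not depend on it.

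**What to change.** 1. In protocol 9.2.2.1, SAP 9.2.2 item 2 and SAP 9.3.2 item 2, make the analysed event the one defined in protocol 3.3.2.1 and SAP 3.2.2. Table 9-1 needs only a matching label.
2. State whether the three parts form one composite, timed at the earliest, or are three separate times. The composite fits the rejection-based criteria in protocol 5.3.2. If they are separate, analyse each.
3. Keep time to first acute rejection of any kind as a supportive analysis under its own label.
4. Specify how treatment status is joined to episodes. Protocol 5.5.2 bases clinical decisions on the local read, while SAP section 4 counts central reads. The derivation must therefore say what happens to an episode treated on the local read but not confirmed centrally.
5. Reconcile protocol 5.5.3.3, which lists reinstitution among the uses of agents to treat rejection, with 5.5.3.4, which places reinstatement after the episode has resolved. This is needed only so that episodes after completed withdrawal can be classified for the analysis. Items 1 to 3 do not depend on it.

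The cost is wording in both documents, possibly amendment review under protocol 9.7, and one programmed derivation. SAP 10.4.4 already lists treatment status for allograft dysfunction episodes.
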